3.3 Biomarkers of thiamine status

Two biomarkers are used to assess thiamine status. Thiamine diphosphate (ThDP) is the biologically active form of the vitamin (4), and concentrations can be assessed in whole blood or erythrocytes using high performance liquid chromatography with a fluorescence detector (27). Unfortunately there is currently no consensus on the most appropriate ThDP cut-offs for thiamine deficiency (28). The other assessment method is a functional marker of thiamine status, transketolase activity coefficient. ThDP is a cofactor with transketolase in the pentose phosphate pathway; *in vitro* measurement of the activity of transketolase before and after the addition of excess ThDP reveals the original level of ThDP saturation, indicating thiamine adequacy (1,25). An erythrocyte transketolase activity coefficient >1.25 is commonly used as a cut-off for thiamine deficiency (1).

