3.7 Summary of rationale

Suboptimal maternal thiamine intake puts exclusively breastfed infants at risk of low thiamine status, impaired cognitive development, and infantile beriberi, which can be fatal. Thiamine fortification of salt is a potentially low-cost and sustainable means of combating suboptimal thiamine status, however knowledge gaps must be filled before thiamine fortification can proceed. There is limited data available on the dose of thiamine required by lactating women to optimize the thiamine concentrations in their milk. Further, usual salt intake among lactating women is unknown. Finally, although there is emerging evidence that low thiamine intake in early life impacts cognitive development, this has yet to be assessed in a controlled research environment. The overall aim of this study is to obtain the information necessary to formulate a thiamine-fortified salt for future use in Cambodia (ideal dose, usual salt intake), and to explore the impact of various doses of maternal thiamine on markers of infant cognitive development.

4. Study Objectives

Primary Outcome and Analysis Objective:

To estimate the dose on the dose response curve where additional maternal intake of thiamine (oral dose) no longer meaningfully increases human milk total thiamine concentration at 24 weeks postpartum.

Secondary Outcomes and Analysis Objectives:

1. To estimate the dose on the dose response curve where additional maternal intake of thiamine (oral dose) no longer meaningfully increases infant thiamine diphosphate concentrations (ThDP) 24 weeks postnatally, and assess whether this depends on the presence/absence of a genetic hemoglobin disorder.
2. To estimate the dose on the dose response curve where additional maternal intake of thiamine (oral dose) no longer meaningfully increases human milk total thiamine concentration at 4 and 12 weeks postpartum.
3. To estimate the dose on the dose response curve where additional maternal intake of thiamine (oral dose) no longer meaningfully increases infant transketolase activity at 24 weeks postnatally, and assess whether this depends on the presence/absence of a genetic hemoglobin disorder.
4. To estimate the dose on the dose response curve where additional maternal intake of thiamine (oral dose) no longer meaningfully increases maternal ThDP at 24 weeks postpartum, and assess whether this depends on the presence/absence of a genetic hemoglobin disorder.

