5. To estimate the dose on the dose response curve where additional maternal intake of thiamine (oral dose) no longer meaningfully increases maternal ETKac at 24 weeks postpartum, and assess whether this depends on the presence/absence of a genetic hemoglobin disorder.
6. To test for differences between the 4 randomised groups on human milk total thiamine at 4, 12, and 24 weeks postpartum.
7. To test for differences between the 4 randomised groups on maternal ThDP at 24 weeks postpartum, and assess whether this depends on the presence/absence of genetic hemoglobin disorder.
8. To test for differences between the 4 randomised groups on maternal ETKac at 24 weeks postpartum and assess whether this depends on the presence/absence of a genetic hemoglobin disorder.
9. To estimate usual household salt intake from mean fortnightly salt disappearance (weight lost, in g).
10. To estimate salt intake among a subset of 100 lactating women, their male partners (if applicable), and their children 24-59 months (if applicable) using observed weighed salt intake records.
11. To estimate sodium intake using 24 hr urinary sodium concentrations among a subset of 100 lactating women.
12. To test for differences between the 0 & 10 mg randomised groups on Composite Mullen and the 5 subscales of the Mullen at 24 and 52 weeks postnatally.
13. To test for differences between the 0 & 10 mg randomised groups on Visual Paired Comparison Novelty Score and the attention and processing speed subscales at 24 and 52 weeks postnatally.

14. To test for differences between the 0 & 10 mg randomised groups on the Language Preference Task Score at 24 and 52 weeks postnatally.
15. To test for differences between 0 & 10 mg randomised groups on oculomotor scores at 24 and 52 weeks postnatally.
16. To determine the effect of inflammation, as measured by C-reactive protein (CRP) and α -1-acid-glycoprotein (AGP) on maternal ThDP at 2 and 24 weeks postpartum, and infant ThDP at 24 weeks postnatal.

5. Study Design

This will be a double-blind, four-parallel arm randomized controlled trial, in which 320 women and their newborn infants will be enrolled. Each dyad will participate in the study between 2 and 24 weeks postnatal, a 22-week intervention period. The primary outcome measure is human milk thiamine concentrations at 24 weeks postpartum (see **Figure 1**). There are additional cognitive assessments at 12 months (52 weeks) postnatal.

[figure not shown]

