2.2 Secondary Objectives

1. To estimate the dose on the dose-response curve where 90% of the maximum average is reached in the following outcomes:
 - a. Infant thiamine diphosphate concentrations (ThDP) at 24 weeks postnatal
 - b. Human milk total thiamine concentration at 4 and 12 weeks postpartum
 - c. Infant transketolase activity coefficient (TKac) at 24 weeks postnatal
 - d. Maternal ThDP at 24 weeks postpartum
 - e. Maternal TKac at 24 weeks postpartumand assess whether this depends on the presence/absence of genetic hemoglobin disorder for the following outcomes:
 - a. Infant ThDP at 24 weeks postnatal
 - b. Infant TKac at 24 weeks postnatal
 - c. Maternal ThDP at 24 weeks postpartum
 - d. Maternal TKac at 24 weeks postpartum
2. To test for differences between the 4 randomised groups on:
 - a. Human milk total thiamine at 4, 12, and 24 weeks postpartum
 - b. Maternal ThDP at 24 weeks postpartum
 - c. Maternal TKac at 24 weeks postpartum

and assess whether this depends on the presence/absence of genetic hemoglobin disorder for the following outcomes:

- a. Maternal ThDP at 24 weeks postpartum
- b. Maternal TKac at 24 weeks postpartum
3. To estimate the usual household salt intake from mean fortnightly salt disappearance (weight lost, in g).
4. In a subset of 100 lactating women, to estimate:
 - a. Salt intake of lactating women, their male partners (if applicable), and their children 24-59 months (if applicable) using observed weight salt intake records
 - b. Sodium intake using 24 hr urinary sodium concentrations in lactating women
5. To test for differences between the 0 mg and 10 mg treatment groups on the following outcomes at 24 and 52 weeks postpartum:
 - a. Composite and 5 subscales of Mullen
 - b. VPC Novelty score and the attention and processing speed subscales
 - c. Language Preference Task scores
 - d. Oculomotor scores
6. To determine the effect of inflammation, as measured by C-reactive protein (CRP) and α -1-acid glycoprotein (AGP) on the following outcomes:
 - a. Maternal ThDP at 2 and 24 weeks postpartum
 - b. Infant ThDP at 24 weeks postnatal

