7.1 Emax curve

Analysis of the primary and several secondary outcomes will be based on the Emax curve.

The Emax curve is defined as:

$$Y = E_0 + E_{\max} \left(\frac{\text{dose}^h}{ED_{50}^h + \text{dose}^h} \right)$$

where E_0 is the baseline concentration without supplementation, E_{\max} is the maximum effect of supplementation, ED_{50} is the dose that produces half of the maximum effect of supplementation and corresponds to the inflection point at which the effectiveness of higher doses starts to decrease, and h is the slope or Hill factor.

The nonlinear Least squares model for the primary outcome will be formulated as:

$$Y = E_0 + E_{\max} \frac{\text{dose}^h}{ED_{50}^h + \text{dose}^h} + \epsilon$$

For secondary outcomes involving testing for effect modification by presence or absence of genetic hemoglobin disorder (GD), additional coefficients (α , β , γ and δ) will be added to all parameters of the Emax curve. The model will be formulated as:

$$Y = (E_0 + E_0\beta\text{GD}) + (E_{\max} + E_{\max}\gamma\text{GD}) \frac{\text{dose}^{(h+h\delta\text{GD})}}{(ED_{50} + ED_{50}\alpha\text{GD})^{(h+h\delta\text{GD})} + \text{dose}^{(h+h\delta\text{GD})}} + \epsilon$$

Evidence of curve shape differences between presence or absence of genetic hemoglobin disorder will be determined by global Likelihood ratio tests. Further testing of the four additional coefficients, in the form of H_0 : coefficient = 0, will be conducted following evidence ($P < 0.05$) from the global test.

The parameter of interest for this study is the dose required to achieve 90% of the maximum concentration (i.e. 90% of $E_0 + E_{\max}$) and this will be estimated from the fitted Emax curve with variance estimated from non-parametric bootstrapping of 100 resamples. For outcomes where there is evidence of curve difference by genetic hemoglobin disorder status ($P < 0.05$ for likelihood ratio test), separate estimates for the dose required to achieve 90% of the maximum concentration with and without genetic hemoglobin disorder will be reported.

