7.3.2 Human milk total thiamine concentration (4 weeks and 12 weeks)

Outcome:	Continuous outcome of total thiamine concentration ($\mu\text{g/L}$) in maternal human milk at 4 weeks and 12 weeks postpartum.
Primary analysis:	Fit a separate Emax curve for 4 and 12 weeks using nonlinear least squares model. Estimate of the dose that reaches 90% concentration (with 95% CI) at each timepoint will be reported.
Secondary analysis:	Fit a linear mixed effects model to outcome at 4, 12, and 24 weeks with treatment group, time, and treatment by time interaction as predictors. Treatment effects (difference in mean total concentration) will be estimated separately for each time point if the interaction p-value is <0.05 and for both time points combined otherwise.
Adjustment:	Health centre, human milk total thiamine at 2 weeks postnatal (linear mixed effects model only)

7.3.3 *Infant transketolase activity coefficient (24 weeks)*

- Outcome: Continuous outcome of infant transketolase coefficient (TKac) at 24 weeks postpartum.
- Primary analysis: Fit an Emax curve using nonlinear least squares approach. Estimate of the dose that reaches 90% concentration (with 95% CI) will be reported.
- Secondary analysis: Fit an Emax curve using nonlinear least squares approach allowing curve to vary by presence/absence of genetic hemoglobin disorder. Estimates of the dose that reaches 90% concentration by genetic hemoglobin disorder status will be reported following evidence from the global test.

7.3.4 *Maternal thiamine diphosphate concentration (24 weeks)*

- Outcome: Continuous outcome of maternal thiamine diphosphate concentration (ThDP; nmol/L) at 24 weeks postpartum.
- Primary analysis: Fit an Emax curve using nonlinear least squares approach. Estimate of the dose that reaches 90% concentration (with 95% CI) will be reported.

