- Secondary analyses: First, fit an Emax curve using nonlinear least squares approach allowing curve to vary by presence/absence of genetic hemoglobin disorder. Estimates of the dose that reaches 90% concentration by genetic hemoglobin disorder status will be reported following evidence from the global test. Second, test for a treatment effect using linear regression and estimate a difference in mean concentration. Third, test for a treatment effect using linear regression with treatment group and treatment by genetic hemoglobin disorder interaction. Treatment effects (difference in mean concentration) will be estimated separately by genetic hemoglobin disorder where the relevant interaction term has a p-value <0.05. Pairwise comparisons will be reported following evidence of a treatment group effect (see Section 5.8). Fourth, test for a linear relationship using linear mixed effects model with CRP at 2 and 24 weeks postnatal, time and treatment group as predictors. Estimate of the mean change (with 95% CI) in ThDP for one unit increase in CRP will be reported. Fifth, test for a linear relationship using linear mixed effects model with AGP at 2 and 24 weeks postpartum, time and treatment group as predictors. Estimate of the mean change (with 95% CI) in ThDP for one unit increase in AGP will be reported.
- Adjustment: Maternal ThDP at 2 weeks postpartum, health centre (linear regressions and mixed effects models only)

7.3.5 *Maternal transketolase activity coefficient (24 weeks)*

- Outcome: Continuous outcome of maternal TKac at 24 weeks postpartum.
- Primary analysis: Fit an Emax curve using nonlinear least squares approach. Estimate of the dose that reaches 90% concentration (with 95% CI) will be reported.

- Secondary analyses: First, fit an Emax curve using nonlinear least squares approach allowing curve to vary by presence/absence of genetic hemoglobin disorder. Estimates of the dose that reaches 90% concentration by genetic hemoglobin disorder status will be reported following evidence from the global test. Second, test for a treatment effect using linear regression and estimate a difference in mean TKac. Third, test for a treatment effect using linear regression with treatment group and treatment by genetic hemoglobin disorder interaction. Treatment effects (difference in mean TKac) will be estimated separately by genetic hemoglobin disorder where the relevant interaction term has a p-value <0.05.

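### The SAP 7.1 dose target has no solution for the transketolase coefficient (two secondary outcomes); separately, the ±1.29 mg/d milk precision carries two confidence levels and settings that cannot be recovered

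*Combined protocol and SAP*

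**What the plan says.** **Transketolase.** SAP 7.1 takes E0 as the level without supplementation and Emax as the maximum effect of supplementation. It then states: "The parameter of interest for this study is the dose required to achieve 90% of the maximum concentration", with 90% of E0+Emax given as the meaning. The variance comes from 100 bootstrap resamples. SAP 2.2 words the secondary objective as "To estimate the dose on the dose-response curve where 90% of the maximum average is reached in the following outcomes" and lists infant and maternal TKac among the outcomes. SAP 7.3.3 has "Continuous outcome of infant transketolase coefficient (TKac) at 24 weeks postpartum" and SAP 7.3.5 has "Continuous outcome of maternal TKac at 24 weeks postpartum". Each is followed by the same instruction as for milk: "Estimate of the dose that reaches 90% concentration (with 95% CI) will be reported". Protocol 3.3 gives the direction of the marker: "An erythrocyte transketolase activity coefficient >1.25 is commonly used as a cut-off for thiamine deficiency". Protocol section 4 nevertheless asks for the dose that "no longer meaningfully increases maternal ETKac at 24 weeks postpartum". For infants it asks for the dose that "no longer meaningfully increases infant transketolase activity at 24 weeks postnatally", naming activity where the SAP analyses the coefficient.

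**Milk precision.** Protocol section 7 and SAP 3.6 report the same simulation of 500 curves: minimum 136 and maximum 210 µg/L, SD 43, and 50% and 90% of the maximum average concentration reached at 1.2 and 2.4 mg/d. Both give ±1.29 mg/d. The protocol attaches it to a 90% interval and the SAP to a 95% interval. Protocol section 11 and the opening of SAP 7 use 95% for reported estimates.

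**The concern.** The 90%-of-maximum target was written for an outcome that rises towards a ceiling. Applied to an outcome that falls towards a floor, it asks for a value 10% below that floor. Two secondary dose objectives, and their versions by genetic hemoglobin disorder, would then return neither an estimate nor an interval. The analyst would have to invent a target. By then the analyst is unblinded (SAP 3.5), and SAP 4.2 requires analyses not specified in the SAP to be identified as post hoc.

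For milk, ±1.29 mg/d is the only precision stated for the primary objective. A reader cannot tell which confidence level, model or number per arm it describes.

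**Working it through.** **1. TKac**

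Set the SAP 7.1 curve equal to its target, with f the fraction of the maximum effect (0 to 1):

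E0 + Emax×f = 0.9×(E0+Emax), so f = [0.9×(E0+Emax) − E0] / Emax.

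For a falling curve Emax < 0, and this becomes

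f = 1 + 0.1×(E0+Emax)/|Emax|.

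This exceeds 1 for any positive plateau E0+Emax. The Emax fraction never exceeds 1, so no dose solves the equation. The algebra needs no TKac values. The documents give none, so those below are assumed, only to show the size:

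| E0 | Plateau | Target | f needed |
|---|---|---|---|
| 1.30 | 1.10 | 0.99 | 1 + 0.110/0.20 = 155% |
| 1.50 | 1.00 | 0.90 | 1 + 0.100/0.50 = 120% |
| 1.15 | 1.10 | 0.99 | 1 + 0.110/0.05 = 320% |

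The same holds within each hemoglobin-disorder group and for every bootstrap resample whose fitted curve falls.

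The literal wording of SAP 2.2 does not rescue it. On a falling curve the maximum average is E0, so the target becomes 0.9×E0 and f = 0.1×E0/(E0 − plateau). That is 0.13/0.20 = 65% for 1.30 to 1.10, 30% for 1.50 to 1.00, and 230% (again no solution) for 1.15 to 1.10. It contradicts SAP 7.1 and marks a 10% fall from placebo, not the approach to a plateau.

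With E0+0.9×Emax instead, f = 0.9 and dose = ED50×9^(1/h), which exists for rising and falling curves alike.

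**2. Milk precision**

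*Inputs as worded.* 50% of 210 = 105 µg/L, below the stated minimum of 136. No curve satisfies this.

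*One feasible repair.* Read 50% as half the effect (ED50 = 1.2 mg/d) and 90% as 0.9×210 = 189 µg/L at 2.4 mg/d. Then f(2.4) = (189−136)/74 = 53/74, and h = ln(53/21)/ln 2 = 1.336. The arm means at 0, 1.2, 2.4 and 10 mg/d are 136, 173, 189 and 205.9.

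*Reproducing ±1.29.* By the delta method with h held fixed and SD 43, the standard error of the target dose is 0.659 at 80 per arm and 0.736 at 64 per arm (80×0.8, borrowing the 20% attrition from the pairwise calculation). Half-widths in mg/d:

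| h fixed, delta method | 95% | 90% |
|---|---|---|
| 80 per arm | 1.96×0.659 = 1.29 | 1.645×0.659 = 1.08 |
| 64 per arm | 1.96×0.736 = 1.44 | 1.645×0.736 = 1.21 |

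So ±1.29 is reproduced as a 95% interval at 80 per arm with h fixed. That does not identify the settings. In repeated 500-run simulations with h fixed, the half-width ranged over 1.22–1.40 (95%, 80 per arm) and 1.16–1.35 (90%, 64 per arm), and 1.29 sits inside both.

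*Another repair.* Put both points on the effect scale: h = ln 9/ln 2 = 3.17. The SAP 7.1 target then falls at 1.61 mg/d, and the 95% half-width with h fixed at 80 per arm is 0.32. The choice of repair therefore matters.

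*If h is estimated.* Four parameters on four doses give a saturated fit. Simulating the h = 1.336 curve at 80 per arm with h free, the median dose estimate was about 2.5 mg/d, the upper quartile about 6 to 9 mg/d, and the upper tail was set by the search limits. No symmetric half-width describes that distribution.

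**The case against.** **On TKac.** The scope is limited. The curves can still be fitted, and maternal TKac keeps its group comparison. A sensible analyst would probably see the problem and adapt. A negative h would also let the equation be solved, but E0 would then be the high-dose level and not the unsupplemented level the SAP defines, and the solution would be a 10% fall from placebo. SAP 5.5 permits transformations when distributional assumptions fail; it does not reverse or redefine a target. The infant activity wording may be loose naming. What stands of this is the limit on scope; none of it supplies a target that works. E0+0.9×Emax is one direction-appropriate choice, and others could be argued.

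**On milk.** The sample size rests on the pairwise calculation (48 per arm, raised to 80), so the simulation describes precision and does not set N. The analysis level of 95% is already fixed elsewhere. This stands and makes the second point minor.

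**Readings to avoid.** A reader might infer that ±1.29 is wrong, or that the 95% match proves the SAP right. The match needs one particular repair of the inputs and a fixed slope, so neither follows. A reader might also infer that the SAP leaves open whether h is estimated in the analysis. It does not: protocol section 11 has the curve parameters estimated by non-linear least squares, and SAP 7.1 gives h no value and attaches a hemoglobin coefficient to it. Only the simulation's setting is unstated.

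**Conclusion.** **Part 1 holds with high confidence and should be fixed.** As written, the target has no solution for TKac whenever the fitted curve falls to a positive plateau. This rests on SAP 7.1's definitions and the direction given in protocol 3.3; the assumed values (120% to 320% of the maximum effect needed) only illustrate. It affects two secondary dose objectives and their hemoglobin-disorder versions. A reader might extend it to milk or ThDP, but those are expected to rise, and nothing here touches their targets or the primary analysis.

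**Part 2 is minor.** The 90%/95% conflict and the impossible 50% input are explicit on the page. The level, slope setting and number per arm behind ±1.29 cannot be recovered. Because the analysis reads as estimating h, ±1.29 is probably too optimistic for the model to be fitted. Confidence in that inference is moderate, since it depends on the repaired curve.

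**What to change.** **TKac only.** In SAP 2.2, 7.1, 7.3.3 and 7.3.5, define the target as the dose reaching E0+0.9×Emax, that is, 90% of the maximum change. State beside it that this is not comparable with the concentration-scale milk and ThDP targets and may be less precise. In protocol section 4, change the maternal ETKac objective from an increase to a decrease, and align the infant wording with the coefficient. Leave the milk estimand as it is.

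**Milk precision.** In protocol section 7 and SAP 3.6, state the scale of the 50% and 90% points. Rerun the existing simulation under the SAP 7.1 model actually to be fitted, with the expected evaluable number per arm. Report the slope setting and that number, and give the result at 95% in both documents. If the estimates are skewed, report percentiles and not a ± figure. Do not change how h is handled in the primary analysis.

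**Cost.** Wording changes and one rerun; no extra participants. The interpretive cost is that TKac doses may look higher than milk doses purely by definition. On the repaired milk curve, used only as an illustration, the two definitions fall at 1.2×9^(1/1.336) = 6.22 and 2.40 mg/d, with 95% half-widths of 3.04 and 1.29 when h is fixed at 80 per arm. The restated milk precision may be less favourable than the present figure.

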The full statistical analysis plan can be found in **Appendix B**. The primary analyses will be performed on an ‘intention to treat’ basis, where all participants will be analyzed according to their allocated treatment group regardless of compliance. A secondary ‘per-protocol’ analysis will be performed on the subset of women who consumed $\geq 80\%$ capsules over the study period. The parameters of the Emax dose-response curves will be estimated using non-linear least squares models. Separate curves will be fitted for outcomes measured at 4 weeks, 12 weeks, and 24 weeks postpartum. The dose where additional maternal intake of thiamine no longer meaningfully increases milk thiamine concentration, defined as the dose that achieves 90% of the maximum concentration, will be estimated from the fitted curve with standard errors estimated by bootstrapping for calculating 95% confidence intervals.

Comparisons between treatment groups will be performed using linear mixed-effects models to account for repeated measurements and adjusted for randomization strata and levels at 2 weeks postnatal. Interaction tests will be performed to assess whether treatment effects depend on genetic hemoglobin disorder. Missing data will be addressed using multiple imputation to create 100 complete datasets for analysis, with a sensitivity analysis performed on the raw (unimputed) data (68). All analyses will follow a pre-specified statistical analysis plan (see **Appendix B**).

12. Administrative Aspects, and Data Security and Management

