3.6 Sample size

To detect a clinically meaningful difference of 40 µg/L in human milk total thiamine concentration between any two treatment groups with 90% power, assuming a SD of 43 µg/L (estimated SD of control group in a Cambodian thiamine-fortified fish sauce trial^[1]) 48 women are required per treatment group, or a total of 192 women. This sample size allows for 20% attrition and is based on a two-sided alpha of 0.0083 for each of the 6 pairwise comparisons between 4 treatment groups to maintain an overall alpha of 0.05. Recruitment of 320 participants (80 per group) was planned to allow for some uncertainty in the assumed values, particularly the SD which may be larger than anticipated.

Simulations of 500 dose-response curves for human milk total thiamine concentration were conducted to estimate the precision that this sample size would provide for addressing the primary study objective (i.e. for estimating the dose required to achieve 90% of the average maximum human milk total thiamine concentration). Data were simulated based on an average minimum and maximum concentration of 136 µg/L^[1] and 210 µg/L^[2] respectively, with a SD of 43 µg/L^[1], and reaching 50% and 90% of the maximum average concentration at dose 1.2 mg/d (EAR group) and 2.4 mg/d (double EAR group) respectively. Assuming a dose-response Emax curve, the precision of the estimated dose is ±1.29 mg/d (i.e. the 95% confidence interval for the estimated dose will be within ±1.29 mg/d of the point estimate).

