4.2 Final analysis and reporting

Once data collection and cleaning is complete, the database will be locked and unblinded treatment codes will be included in the database; a blinded analysis is not possible for estimating dose response curves.

Due to the time-consuming nature of coding video-recorded cognitive assessments, data for the following assessments will not be included in the database before it is locked and unblinded: primary engagement task, secondary engagement task, Visual Paired Comparison Task, and Language Preference Task. Note that the research assistants coding the videos for these assessments will remain blinded.

Analysis of all primary and secondary outcomes will be performed as described in this SAP and the results of the statistical analyses will be made available to the Principal Investigator.

Any post-hoc, exploratory analyses which were not specified in this SAP will be clearly identified in the final report.

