5.3 Methods for withdrawals, missing data and outliers

All available data collected up until time of withdrawal will be included in the statistical analysis.

Multiple imputation using chained equations will be performed separately by randomised treatment group to address missing data under a missing at random assumption. A total of 100 imputations will be performed to ensure $<1\%$ loss of power compared to full information maximum likelihood^[3]. Covariates pre-specified for adjustment in the analysis will be included in the imputation model, along with other auxiliary variables useful for improving the prediction of missing values. Conclusions will be based on the results obtained using imputed data, with sensitivity analyses performed on unimputed data.

Outliers will not be excluded from the primary analysis unless a data entry error is confirmed.

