7.2 Primary outcome variable

7.2.1 Human milk total thiamine concentration (24 weeks)

Outcome:	Continuous outcome of total thiamine concentration ($\mu\text{g/L}$) in maternal human milk at 24 weeks postpartum.
Analysis:	Fit an Emax curve using nonlinear least squares approach. Estimate of the dose that reaches 90% concentration (with 95% CI) will be reported.

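### The primary 95% CI for the target dose rests on a 100-resample bootstrap standard error of a skewed estimate, with fit bounds and imputation order unset; a percentile interval is cheap and avoids impossible limits

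*Combined protocol and SAP*

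**What the plan says.** SAP 7.2.1 makes the dose and its interval the primary result: "Estimate of the dose that reaches 90% concentration (with 95% CI) will be reported". SAP 7.1 defines the target as the dose reaching 90% of E0 + Emax on a curve with four parameters (E0, Emax, ED50, h), fitted by nonlinear least squares to doses 0, 1.2, 2.4 and 10 mg. It says that the dose "will be estimated from the fitted Emax curve with variance estimated from non-parametric bootstrapping of 100 resamples". Protocol section 11 says that the dose "will be estimated from the fitted curve with standard errors estimated by bootstrapping for calculating 95% confidence intervals".

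Neither document gives an interval formula, bounds for h or ED50, a rule for fits that fail, or a rule for doses above 10 mg. The one convergence clause, in SAP 5.6, allows confounders to be dropped, but the primary fit has none. SAP 5.3 adds 100 imputations by arm: "Conclusions will be based on the results obtained using imputed data, with sensitivity analyses performed on unimputed data". It does not say whether to bootstrap within imputations or impute within resamples. SAP 4.2 notes that "a blinded analysis is not possible for estimating dose response curves".

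**The concern.** The target dose is read off a curve that is flat near its top. When a resampled curve is still rising at 10 mg, the inverted dose becomes very large. A standard error then mixes a tight central cluster with a long upper tail, and a symmetric interval reflects that tail below the estimate, past zero. How long the tail is depends on the values of h and ED50 that the fit may visit, which the SAP leaves open. Two analysts following the SAP faithfully could report materially different intervals for the primary objective.

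**Working it through.** **Inputs (SAP 3.6).** Minimum 136 and maximum 210 µg/L, so E0 = 136 and Emax = 74; SD 43; 80 per arm, or 64 after 20% loss. The curve is described as "reaching 50% and 90% of the maximum average concentration at dose 1.2 mg/d" and 2.4 mg/d respectively. Taken literally, 50% of 210 is 105, below the minimum of 136, so I assume shares of the rise. Then ED50 = 1.2 and h = ln 9 / ln 2 = 3.17.

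**The plan's own figures.** The sample size reproduces: 40 µg/L, SD 43, 90% power and alpha 0.0083 need 38 per group by the noncentral t, and 38/0.8 = 47.5, rounded up to 48. The ±1.29 mg/d precision was not reproduced. At 80 per arm the half-range of simulated estimates is 0.74 mg (95%) or 0.54 mg (90%) for the SAP 7.1 target. The nearest variant, 1.96 × SD with doses capped at 10 mg, gives 1.21.

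**True target.** 0.9 × 210 = 189. Share of the rise = (189 − 136)/74 = 0.716, odds 2.524. Dose = 1.2 × 2.524^(1/3.17) = 1.61 mg.

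**Reversed top arms.** Expected means at 2.4 and 10 mg are 202.6 and 209.9, a difference of 7.31.
- Between trials at 80 per arm: SE = 43 × √(2/80) = 6.80; Φ(−7.31/6.80) = 14%.
- Resamples, averaged over trials: SD = 6.80 × √2 = 9.62; Φ(−7.31/9.62) = 22%.
- At 64 per arm: 17% and 25%. Simulated resample shares were 22–26%.

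In these cases an unbounded fit has no finite h. A Gauss-Newton fit started at the true values failed in 15–16% of trials. As h grows, ED50 × 2.524^(1/h) tends to 1.2 mg; bounded fits gave a median of about 1.3 mg.

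**Skew.** At 80 per arm the 2.5th, 50th and 97.5th percentiles of the estimate are 1.25, 1.60 and 2.66 mg. Its SD is 2.2 mg with h 0.5–10 and ED50 0.01–15, but 309 mg with h 0.1–50 and ED50 0.01–100.

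**Intervals.** Complete data, normal errors, resampling within arm. Ranges span separate runs of 300 to 2,000 trials with slightly different bounds; 64 per arm is in brackets.

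| Interval | Lower limit below 0 mg | Half-width over 10 mg | Coverage |
|---|---|---|---|
| ±1.96 SE, 100 resamples, h below 1 allowed | 36–43% (45–49%) | 22–33% (30–40%) | 91–94% (93–95%) |
| ±1.96 SE, h at least 1 | 7–11% (13–16%) | about 0% | 90% (92%) |
| Percentile, 1,000 resamples, h below 1 allowed | never | 11.5–17% (17–24%) | 94–95% (93–96%) |

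With h below 1 allowed:
- Median half-width, SE against percentile: 0.78–0.88 against 0.64–0.70 mg at 80 per arm; 1.06–1.44 against 0.79–0.90 mg at 64.
- Misses at 80 per arm (2,000 trials): the SE interval lies too high in 0.1% and too low in 6.4%; the percentile interval in 3.0% and 1.8%.
- Percentile with only 100 resamples: coverage 93.5% (91.8%), no gain over the SE interval's 93.5% (93.4%) in the same runs.
- Same data, h from 0.5 against h from 1: the SE half-width more than doubles in 37% of trials (45%), although the median ratio is 1.02 at 80 per arm.
- Dropping non-monotone resamples moves SE-interval coverage from 93.5% to 96.5% at 80 per arm.

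**Order of bootstrap and imputation (illustration).** Assumptions: 10% / 20% missing completely at random, a 2-week covariate correlated 0.5 with the outcome, 80 per arm. The SE lower limit is below 0 in 50% / 58% when imputing inside each resample, and in 78% / 79% with Rubin's rules on the raw dose (200 trials). The percentile interval with one imputation per resample covers 96% / 97%, with an upper limit over 10 mg in 27% / 33%.

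**The case against.** **Coverage is already near nominal.** This stands. A reader might infer that the planned interval seriously under-covers, or that the percentile interval covers better. Neither is supported: at 64 per arm one comparison gave 93.4% (SE) against 93.2% (percentile), and at 80 per arm the gain is only a point or two.

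**The extreme widths come from allowing h below 1.** This also stands: with h at least 1 they vanish. But the SAP sets no such bound, and imposing one is risky. With a true h of 0.7 (my assumption; the planning curve implies 3.17), a percentile interval with h held at 1 or more covers 54%.

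**A negative limit can be read as not distinguished from placebo.** It cannot safely be read so. It arises because upper-tail uncertainty is mirrored downwards, and the percentile limit from the same data is not negative.

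**±1.96 SE is an inference.** True: no formula is written, and an SE on log dose would also fit the text. That version is never negative, but it covers 90–92% under the planning curve and 83–84% if the true h is 1 or 0.7 (assumed).

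**Reversed means do little harm.** Largely true. A reader might infer that about a fifth of resamples yield no dose. In fact h diverges but the dose settles near 1.2–1.3 mg. Keeping or dropping those resamples changes the share of percentile upper limits over 10 mg only from 20% to 21%.

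**Much of this is design.** Four parameters on four doses, with none between 2.4 and 10 mg, leave uncertainty that no interval method removes.

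**Unblinding.** SAP 4.2 says that the analysis is unblinded. It does not say that fitting rules will be chosen then; they are simply not fixed beforehand.

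**Conclusion.** The concern holds as a weakness of method and specification in the primary interval. If the standard error is used symmetrically on the dose scale and h may fall below 1, over a third of trials at 80 per arm would report an impossible lower limit, and between a fifth and a third a half-width above 10 mg. Both figures depend heavily on bounds that the SAP omits. A 1,000-resample percentile interval never goes negative, is narrower at the median and has better-balanced misses, at about equal coverage.

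This rests on the SAP 3.6 inputs, the shares-of-the-rise reading, normal errors and within-arm resampling. A reader might conclude that the stated ±1.29 mg/d is wrong. The documents do not support that, because the figure depends on unstated bounds and failed-fit handling. Nor should the result be carried to the secondary Emax outcomes: ThDP was not simulated, and the transketolase target raises a separate question of definition.

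**What to change.** In SAP 7.1, aligned with protocol section 11 and SAP 5.3, replace the bootstrap-variance sentence for the primary milk thiamine outcome with:

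> The 95% CI is the 2.5th and 97.5th percentiles of the target dose over at least 1,000 bootstrap resamples drawn within arm, with missing values imputed by arm once inside each resample before refitting. Every fit uses bounds on h and ED50 that are fixed before unblinding and allow h below 1 (for example h 0.5–10, ED50 0.1–10 mg). Non-converged fits are redone by grid search within the bounds; fits at a bound are kept and counted. A limit above 10 mg is reported as beyond the tested range.

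Add one rule for a fit with no rising curve, the same for estimate and interval, and report a fit with h of at least 1 as a sensitivity analysis. The definition of the point estimate need not change.

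The cost is the wording and computing time; about 2 million bootstrap fits ran in roughly a minute. The downside is that upper limits beyond the tested range will appear in about 15–20% of planning-curve trials at 80 per arm and 23–27% at 64. They will be more frequent with imputed data, and in 91–94% of trials if the true curve is shallow (assumed h of 1 or 0.7). One imputation per resample is slightly conservative. The increase to about 1,000 resamples is essential, since 100 gave no coverage gain.
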